### **9.3.3.3.** Exploratory outcomes

#### 9.3.3.3.1. All-cause mortality

The exploratory all-cause mortality outcome will evaluate the time to death, as recorded in the database.

### 9.3.3.3.2. Change in UACR values over time

The exploratory analysis of UACR values over time will be performed in the analysis set of those with available baseline UACR values. Recorded UACR values during follow-up will be identified to describe changes in UACR over time, specifically at 4 months and 12 months of follow-up.

#### 9.3.4. Covariate definitions

Covariates include risk factors for renal progression [39,40], cardiovascular outcomes [41,42], or hyperkalaemia [43-45]. Variables potentially associated with the use or non-use of finerenone and the outcomes of interest—e.g., concomitant medications, comorbidities—will be identified for all cohort members before or on Time 0 using diagnosis, procedure, or medication information available in the data source. A detailed description of definitions and code lists for all covariates that will be used in the data source will be specified in the SAP. Covariates will be defined using ICD-10-CM diagnosis codes, laboratory records, procedure coding, or medication coding, as appropriate for each variable.

The following demographic characteristics will be evaluated as of Time 0:

- Age
- Sex
- Calendar year of Time 0
- Race and/or ethnicity (as available in the data)
- Socioeconomic status (as available in the data)
- US geographic region
- Insurance plan type

The following clinical characteristics of patients will be defined using the 365 days before and including Time 0, except where specified otherwise:

- Markers of T2D severity (as available in the data source) and components of the Diabetes Severity Complications Index [46,47] not listed elsewhere
  - Duration of T2D (in all available lookback, as available in the data source)
  - Insulin use
  - Haemoglobin A1c (glycated haemoglobin) (HbA1c) (most recent recorded laboratory value in the 183 days before and closest to Time 0, if available)
  - Hyperosmolar hyperglycaemic state
  - Ketoacidosis

- Lower limb amputations (all available lookback, as available in the data source)
- Neuropathy
- Retinopathy
- Markers of kidney dysfunction severity
  - Duration of CKD (all available lookback, as available in the data source)
  - CKD stage, defined based on eGFR, or stage-specific diagnosis codes (using all available lookback) (Section 9.3.1)
  - Albuminuria stage defined based on UACR values (Section 9.3.1)
  - Proteinuria, defined based on diagnosis codes (Section 9.3.1)
  - Nephrotic syndrome, based on diagnosis codes (Section 9.3.1)
  - Glomerulonephritis
  - Renovascular disease
  - Polycystic kidney disease
  - Autoimmune disease
  - Gout/hyperuricaemia
  - Hospitalisation episodes for acute kidney injury

The following comorbidities will be defined using all available lookback before and including Time 0:

- Cardiovascular comorbidities
  - Acute myocardial infarction
  - Atherosclerosis
  - Atrial fibrillation
  - Cerebrovascular disease (stroke or transient ischaemic attack)
  - Congestive heart failure
  - Hypercholesterolaemia
  - Hyperlipidemia
  - Hypertension
  - Peripheral vascular disease
  - Unstable angina
- Other components of the Charlson Comorbidity Index or similar comorbidity score [48,49] (as single entities, not listed elsewhere)
  - Anaemia
  - Chronic obstructive pulmonary disease
  - Congestive heart failure
  - Dementia

- Human immunodeficiency virus
- Liver disease
- Malignancy other than kidney cancer or nonmelanoma skin cancer
- Paralysis
- Other comorbidities
  - Coronavirus disease 2019 (COVID-19) diagnosis
  - Hyperkalaemia (history of hyperkalaemia, more than 90 days before Time 0)
  - Osteoporosis
  - Pneumonia

The following lifestyle cardiovascular factors will be defined, as available in the data:

- Body mass index or evidence of obesity
- Smoking status
- Alcohol abuse

The following healthcare utilisation measures will be identified in the 365 days before and including Time 0 to characterise patients' healthcare access, healthcare-seeking behaviour, and indicators of disease state at the time of index medication initiation:

- Healthcare utilisation
  - Hospital visits and hospital admissions
  - Emergency department visits
  - Long-term care or skilled nursing facility residence
  - Number of eGFR laboratory tests performed
  - Number of serum potassium laboratory tests performed
- Preventive health services
  - Influenza vaccination
  - Pneumococcal vaccination
  - COVID-19 vaccination
  - Bone mineral density test
  - Screening mammogram
  - Other cancer screening
- Frailty indicators [50]
  - Arthritis
  - Bladder dysfunction
  - Dementia
  - Psychiatric illness
  - Weakness
  - Vertigo

The following comedications will be identified in the 183 days before and including Time 0 to characterise individuals' recent treatments and indicators of disease state at the time of index medication initiation:

- Medications for T2D
  - Alpha glucosidase inhibitors
  - Dipeptidyl peptidase-4 inhibitors (DPP-4i)
  - GLP-1 RA
  - Meglitinides
  - Metformin
  - SGLT2i
  - Sulfonamides
  - Sulfonylureas
  - Thiazolidinediones
  - Insulin
- Cardiovascular medications
  - Angiotensin-converting enzyme inhibitors/angiotensin receptor blockers (ACEi/ARBs)
  - Aldosterone receptor blockers
  - Angiotensin receptor-neprilysin inhibitor
  - Anticoagulants
  - Aspirin and other antiplatelets (e.g., clopidogrel, ticlopidine, prasugrel)
  - Beta-blockers
  - Digoxin
  - Direct renin inhibitors
  - MRAs, other than finerenone
  - Nitrates and other vasodilators
  - All calcium channel blockers
  - Lipid-lowering drugs
  - Loop diuretics
  - Other antihypertensives
  - Potassium-sparing diuretics
  - Thiazide-like diuretics
  - Statins
  - Potassium Binders
- Other medications
  - Acetaminophen

- Anti-inflammatory drugs
- Anticonvulsants
- Antibiotics, antifungals, and antituberculars
- Bronchodilators
- Calcineurin inhibitors
- Chemotherapeutic agents
- Non-steroidal anti-inflammatory drugs

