#### 9.2.1.2. Selection criteria

Individuals must meet all the following inclusion criteria on or before Time 0 to be included in the cohort:

- Active registration or continuous enrolment for at least 365 days in the data source before Time 0 (days [-365, 0])
- No recorded use of finerenone before Time 0 (days [-all available, 0])
- Aged 18 years or older on Time 0
- Diagnosis of T2D at any time on or before Time 0 (days [-all available, 0])
- Evidence of CKD on or before Time 0 (days [-all available, 0]), identified by meeting any of the following criteria:
  - A diagnosis code indicating CKD stage 1, 2, 3, 4, or stage unspecified
  - Two UACR test results  $\geq$  30 mg/g separated by at least 90 days and no more than 540 days.
  - Two different eGFR test results  $\geq 15 \text{ mL/min}/1.73 \text{ m}^2 \text{ AND}$ < 90 mL/min/1.73 m^2 [17] separated by at least 90 days and no more than 540 days. If a reported eGFR test result is available in the data, it will be used as recorded to determine eligibility (as that was the eGFR value available to the prescribing clinician at the time of Time 0). If an eGFR value is not reported, but there is sufficient information to calculate the eGFR, it will be calculated using the creatinine-based 2021 CKD-EPI equation [18] (Section 9.3.1).

Individuals will be excluded if they meet any of the following exclusion criteria on or before Time 0:

- Type 1 diabetes (T1D) at any time on or before Time 0 (days [all available, 0]), as finerenone is not indicated for use in T1D
- Evidence of end-stage kidney disease (ESKD) at any time on or before Time 0 (days [all available, 0]) —as finerenone is not recommended to be initiated in individuals with ESKD or severely reduced eGFR—identified as any of the following criteria:
  - Two different eGFR test results < 15 mL/min/1.73 m^2 [17] separated by at least 90 days and no more than 540 days
  - Dependence on dialysis (at least 3 sessions over at least 90 days)
  - A diagnosis code indicating kidney failure or CKD stage 5 (International Classification of Diseases, 10th Revision, Clinical Modification [ICD-10-CM] code N18.5)
  - A diagnosis code indicating having a kidney transplant (ICD-10-CM code Z94.0)
- Diagnosis of kidney cancer at any time on or before Time 0 (days [-all available, 0]), as decreased renal function resulting from kidney cancer may differ in treatment response from diabetic CKD.

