### 9.2.1.3. Follow-up

Individuals will be followed-up from the day after Time 0 (i.e., day 1) until the first occurrence of 1 of the following:

- The date of an occurrence of the study outcome under evaluation (each outcome will be evaluated separately, and individuals may have different follow-up times for each outcome)
- Censoring at any of the following events:
  - End of the study period (i.e., end of available study data)
  - Loss to follow-up in the data source
  - Deviation from the treatment strategy defined on Time 0 for the primary analysis
    - Finerenone-exposed individuals discontinuing use of finerenone for reasons other than hyperkalaemia (pausing or discontinuing treatment for elevated serum potassium is consistent with treatment dose adjustment strategies [13]) or ESKD (discontinuing treatment for ESKD is consistent with treatment recommendations) [22]
    - Nonusers initiating finerenone

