### 9.4. Data sources

This study will be conducted using existing healthcare data from the US. Considered data sources include the HealthVerity® Chronic Kidney Disease Masterset. This data source includes closed administrative health insurance enrolment, medical claims, and pharmacy claims data supplemented with laboratory test results, electronic medical record information, and mortality records. The Masterset contains information on over 10 million unique patients with evidence of CKD in the US with commercial, Medicare Advantage, or Medicaid insurance coverage.

Additional data sources may be considered to increase the sample size or representativeness of the study sample. If multiple data sources are used, meta-analytic methods may be considered, as appropriate, to generate summary estimates across data sources. Should additional data sources be added, the data source will be recorded and described in an update of the protocol, and a data source–specific SAP will be prepared to describe and document any data source–specific adaptations.

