#### 9.7.7. Sensitivity analyses

#### 9.7.7.1. Negative control analysis

To evaluate the potential for unmeasured confounding and other residual bias, a negative control outcome analysis will be performed. Negative control outcomes should not be causally related to the exposure, but as much as possible, should have the same set of common causes as the study exposure-outcome association being evaluated [62]. The outcomes being evaluated (cardiovascular and kidney outcomes) may also be influenced by other behavioural factors that are difficult to measure in existing healthcare data, such as diet, exercise, or other lifestyle factors; healthcare-seeking behaviour; or adherence to medications. Thus, potential negative control outcomes to assess the impact of unmeasured confounding by these factors would also require some association with healthy lifestyle.

A negative control outcome will be selected using the following criteria:

- The outcome should not be caused by finerenone use, directly or indirectly; thus, any outcomes with known associations, signals detected in pharmacovigilance systems, or published case reports will not be considered.
- The outcome should be severe (requiring hospitalisation or emergency department admission) to match the severity of the primary outcomes.
- The outcome should be reasonably common, matching the expected incidence of the outcomes of interest in this population.

Initially considered negative control outcomes may include the following:

- Hospitalisation or emergency department visit for asthma
- Laceration of hand or finger

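### Protocol 9.3.4 lists no measure of prior medication adherence, although the protocol names adherence as an influence on the outcomes and its pharmacy claims could supply one; one-sided censoring at discontinuation makes the gap matter more

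*Protocol*

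**What the plan says.** **Covariates.** Protocol 9.3.4 says it will identify "Variables potentially associated with the use or non-use of finerenone and the outcomes of interest". The medication part opens "The following comedications will be identified in the 183 days before and including Time 0" and then lists drug classes. Nothing in the section measures adherence, persistence or days covered before Time 0. What it leaves to the SAP is definitions and code lists for the covariates.

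**Adherence as a bias source.** Section 9.7.7.1 says the outcomes may be influenced by "behavioural factors that are difficult to measure in existing healthcare data". Its examples end with "healthcare-seeking behaviour; or adherence to medications". The response there is a negative control outcome.

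**Data.** Section 9.4: "This data source includes closed administrative health insurance enrolment, medical claims, and pharmacy claims data". Section 9.2.1.2 requires "Active registration or continuous enrolment for at least 365 days in the data source before Time 0".

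**Censoring.** Section 9.2.1.3 censors "Finerenone-exposed individuals discontinuing use of finerenone for reasons other than hyperkalaemia" or ESKD. In the comparator group, the only treatment deviation is starting finerenone (9.2.1.3 and 9.3.2.2).

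**Weights.** Section 9.7.2 builds the propensity score from prespecified baseline characteristics. Section 9.7.3 recognises that differential censoring can cause selection bias. It plans inverse probability of censoring (IPC) weights with time-varying predictors and leaves their full description to the SAP.

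**The concern.** Patients who take long-term drugs reliably may have fewer cardiovascular events for reasons unrelated to finerenone. Adherence can then enter the comparison in two ways.

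1. **Confounding at Time 0.** Initiators of a new drug may already be better adherers than nonusers.
2. **Selection during follow-up.** Poor adherers may stop finerenone sooner and be censored, which enriches that arm for good adherers. The comparator arm has no equivalent filter.

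Weights correct for adherence only through variables in their models. The protocol's list contains proxies for health behaviour but no direct measure, although fills of established drugs are in the data. Section 9.3.2 already plans to estimate finerenone discontinuation from prescribing and dispensing records, so the study relies on similar records for persistence after Time 0.

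A bias of a few percent matters because random error will be small. Section 9.5 expects at least 20,000 initiators.

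**Working it through.** **1. The protocol's own precision figure.** Section 9.5 assumes RR 0.86 at 10:1, with comparator risk 14.4% or 7.2%. It states a probability above 80% that the 95% CI excludes 1, at 30,000 and 60,000 records. A pooled two-proportion calculation (two-sided 0.05) gives 83.2% (2,727 against 27,273) and 80.2% (5,455 against 54,545). The stated figures reproduce and this point does not change them.

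**2. Random error at the expected size.** Take 20,000 initiators, 200,000 comparator records, RR near 1 and no allowance for weighting or repeated Time 0s. The standard error of log RR is √[(1−p)/(20,000p) + (1−p)/(200,000p)].
- p = 0.144: 95% limits around 1 are about 0.965 to 1.036.
- p = 0.072: about 0.949 to 1.054.

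Weighting and repeated records would widen these limits.

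**3. Illustrative bias model.** The documents give no adherence share, stopping rate or adherer effect, so these inputs are assumptions:
- two classes, high and low adherers; 50% high among nonusers; 50%, 60% or 65% high among initiators;
- event hazard h = 0.05 per year in low adherers (9.5 implies a similar order: 0.144/3.0 = 0.048 per year) and 0.65, 0.75 or 0.85 times that in high adherers;
- finerenone stopping rate c = 0.25 per year (high) and 0.90 per year (low), with every stop censored; c = 0 in nonusers;
- T = 1.5 years, no true effect, and no correction by any other covariate or weight.

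Person-time per head is PT = (1 − e^(−(h+c)T))/(h+c). The arm rate is Σ(share × h × PT)/Σ(share × PT), and the apparent HR is approximated by the ratio of arm rates.

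At hazard multiplier 0.75 (high-adherer hazard 0.0375):
- PT on finerenone: high 1.218, low 0.799. PT in nonusers: high 1.459, low 1.445.
- Nonuser rate: (0.5×0.0375×1.459 + 0.5×0.05×1.445)/(0.5×1.459 + 0.5×1.445) = 0.04372.
- **Censoring alone (50% high in both arms):** (0.5×0.0375×1.218 + 0.5×0.05×0.799)/(0.5×1.218 + 0.5×0.799) = 0.04245; ratio 0.971.
- **Baseline imbalance alone (60% against 50%, no censoring):** ratio 0.971.
- **Both:** (0.6×0.0375×1.218 + 0.4×0.05×0.799)/(0.6×1.218 + 0.4×0.799) = 0.04130; ratio 0.945.

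Each route contributes about half of the combined figure. Full grid under a true null:

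| High adherers among initiators | 0.65 | 0.75 | 0.85 |
|---|---|---|---|
| 50% (censoring alone) | 0.957 | 0.971 | 0.984 |
| 60% | 0.918 | 0.945 | 0.969 |
| 65% | 0.900 | 0.932 | 0.962 |

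(Columns: high-adherer hazard multiplier.)

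**4. Sensitivity.** If low adherers stop at 0.45 instead of 0.90 per year, censoring alone gives 0.986 to 0.995. A separate model solved the Cox score equation with equal adherence at Time 0, stopping at 0.3 per year in adherers and 0.6 to 2.0 in non-adherers, and adherer hazard 0.5 to 0.85 times. It gives 0.86 to 0.99. With equal adherence at Time 0 and stopping unrelated to adherence, it gives exactly 1.00.

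**The case against.** Four arguments on the other side have weight.

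- **The SAP may deal with it.** IPC weights are the protocol's tool for selection by censoring, and their variables are deferred to a document not at hand. A reader might infer that neither the propensity weights nor the censoring weights can correct the problem. The documents do not support that: the SAP may add adherence to the IPC model.
- **Proxies and checks exist.** Section 9.3.4 lists vaccinations, screening, utilisation, laboratory test counts, frailty indicators and HbA1c. Section 9.7.3 places the negative control analysis before the primary analyses. Section 9.9 admits that unmeasured confounding may remain.
- **Direction is not established.** A reader might infer that the primary HR is certain to be biased towards finerenone. That requires low adherers both to stop sooner and to have more events. Section 9.9 itself describes an opposing bias, from users at more advanced disease stages, so the net direction is unknown.
- **Size is not established.** A reader might also infer a bias close to the assumed effect of 0.86. The worst grid value, 0.90, is ln(0.90)/ln(0.86) = 70% of that effect on the log scale. It needs the extreme inputs together and no help from any other covariate. Censoring alone at the central inputs is ln(0.971)/ln(0.86), about 20%. The model also censors every stop, whereas the protocol does not censor stops for hyperkalaemia or ESKD.

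The omission itself remains. The protocol fixes which baseline covariates are listed. Section 9.7.7.1 names healthcare-seeking and adherence as separate factors, so proxies for the first need not capture the second. A negative control can signal bias but cannot remove it.

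**Conclusion.** The point holds as an avoidable gap, not as a demonstrated bias. Section 9.3.4 omits a factor that 9.7.7.1 says may influence the outcomes. The stated difficulty of measurement does not fit 9.4 and 9.2.1.2 for drugs the patient already takes. Because only the finerenone arm is filtered on persistence, healthy-adherer confounding and selection may favour finerenone, to the extent that the proxies and the SAP's IPC variables leave adherence uncaptured.

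Under the assumptions shown and with no such capture, a true null would appear as about 0.96 to 0.98 from one-sided censoring alone, and 0.90 to 0.97 with 60 to 65% high adherers among initiators against 50% among nonusers. The central combined value of 0.945 lies just beyond the simple unweighted limits around 1 at 20,000 initiators. The true size cannot be known from the documents. This is a worthwhile, inexpensive improvement.

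**What to change.** Add to 9.3.4 the proportion of days covered in the 365 days before Time 0 for ACEi/ARB, statins and oral glucose-lowering drugs, averaged over the classes used, with a separate category for patients on none of them. Include it in the propensity models and as a baseline predictor in the IPC models of 9.7.3. Report its balance before and after weighting. Reword 9.7.7.1 so that adherence to established drugs is no longer treated as hard to measure.

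The cost is a little programming on claims already held; no endpoint or eligibility rule changes. The measure is undefined for patients without a chronic drug, hence the separate category, and is less accurate where only EHR prescription records exist.

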### 9.4. Data sources

This study will be conducted using existing healthcare data from the US. Considered data sources include the HealthVerity® Chronic Kidney Disease Masterset. This data source includes closed administrative health insurance enrolment, medical claims, and pharmacy claims data supplemented with laboratory test results, electronic medical record information, and mortality records. The Masterset contains information on over 10 million unique patients with evidence of CKD in the US with commercial, Medicare Advantage, or Medicaid insurance coverage.

Additional data sources may be considered to increase the sample size or representativeness of the study sample. If multiple data sources are used, meta-analytic methods may be considered, as appropriate, to generate summary estimates across data sources. Should additional data sources be added, the data source will be recorded and described in an update of the protocol, and a data source–specific SAP will be prepared to describe and document any data source–specific adaptations.

### 9.5. Study size

For the primary effectiveness composite cardiovascular outcome, the precision of the relative risk (RR) estimates was estimated with assumptions based on results from a combined analysis of pivotal randomised trials of finerenone [8,11,12]. The composite cardiovascular outcome used in those trials differed slightly from the outcome proposed in this study (the trial outcome included nonfatal stroke and all cardiovascular death). The sample size estimate for the current study assumed a RR of 0.86 (the hazard ratio [HR] for the composite outcome, as noted in the combined analyses [12], acknowledging that HRs for the individual components of the trial composite outcome included in this study's composite outcome were all similar, ranging from 0.78 [hospitalisation from heart failure] to 0.91 [nonfatal myocardial infarction]).

The risk of the composite cardiovascular outcome in the comparator group in the combined trial data was 14.4% [12] over up to 4 years of follow-up (median follow-up of 3.0 years) [12]. Because the trial composite outcome included additional components not included in the current study, standard care has evolved since the trial, and the follow-up time of the current study may be less than the median of 3 years in the trial, assumptions of risk in the comparator group of 14.4% (observed in the trial) and a reduced estimate of 7.2% were considered.

With these assumptions of outcome occurrence, the estimated precision of RR estimates in sample sizes ranging up to 50,000 were estimated with an assumed comparator-to-finerenone user ratio of 10:1. For the effectiveness outcomes, the probability of the upper limit of the 95% confidence interval (CI) being below 1 was estimated, as the intention of those analyses

was to evaluate real-world effectiveness. Sample size calculations were performed with EpiSheet [51].

[figure not shown]

Figure 3: Precision of estimated risk ratios for the composite cardiovascular outcome at an array of sample sizes

CI = confidence interval.

The RR precision estimates for the primary cardiovascular effectiveness outcome are shown in Figure 3. Under these assumptions, there would be a greater than 80% probability of the 95% CI of the RRs to exclude 1 at total sample sizes of approximately 30,000 included records (2,727 finerenone users, and the rest comparators) for the higher estimate of composite cardiovascular outcome incidence and 60,000 records (5,455 finerenone users) for the lower estimate of composite cardiovascular outcome incidence. For secondary effectiveness and safety outcomes with lower expected incidence, larger sample sizes would be required to achieve the same level of precision.

Based on initial feasibility assessments in the HealthVerity® Chronic Kidney Disease Masterset, we are expecting to include at least 20,000 individuals initiating finerenone. Although no specific feasibility was conducted to assess the number of patients with CKD and T2D fulfilling the criteria for finerenone prescription, based on current prescription patterns of finerenone, we are expecting the number of potential individuals in the comparator group to far exceed those required for this study.

